## **9.3 Data collection**

[figure not shown]
For studies using Electronic Data Capture (EDC), the designated investigator staff will enter the data required by the protocol into the Electronic Case Report Forms (eCRF). The eCRFs

have been built using fully validated secure web-enabled software that conforms to 21 CFR Part 11 requirements, Investigator site staff will not be given access to the EDC system until they have been trained. Automatic validation programs check for data discrepancies in the eCRFs and, allow modification or verification of the entered data by the investigator staff.

The Principal Investigator is responsible for assuring that the data entered into eCRF is complete, accurate, and that entry and updates are performed in a timely manner.

### **9.3.1 ECG data collection**

ECG data will be collected via 12-lead digital ECG machines and analyzed locally.

#### **9.3.4 IRT data collection**

Patient eligibility and enrollment will be tracked using an Interactive Response Technology. The system will be supplied by a vendor, who will also manage the database for that system.

#### **9.3.5 Central laboratory**

Following protocol amendment 6, laboratory samples will be collected and analyzed locally and the results will be entered directly into the CRF.

#### **9.3.6 Central radiology**

Radiological imaging and photography data will be acquired by the sites and interpreted locally. Additionally, radiological and photography data will be transmitted by the sites to the CRO designated by Novartis to undergo quality checks and central review by a blinded independent review committee (BIRC). The BIRC will perform an assessment of PFS data for a randomly selected subgroup of patients. An independent random sampling process will select all scans (and relevant information) from approximately 40% of randomized patients (see [Section 10.8](#)), whose BIRC randomization identity will be unknown to the investigators. If consistency of treatment effect is not established, the BIRC may perform an assessment of PFS data for all patients.

Tissue and fluid collections results and pre-existing radiographic findings will be recorded in the eCRF and may be transmitted to the imaging CRO for review if appropriate. Further details regarding BIRC assessment will be provided in the BIRC charter. The central review of the

scans will be carried out in a blinded fashion. The decision regarding patient management will remain with the local investigator.

Note: Once the radiology review from the blinded independent review committee has been completed, patients' radiological and photography data images should no longer be transmitted to the imaging CRO. Novartis will notify all sites when central imaging submission for the trial is complete.

#### **9.4 Database management and quality control**

For studies using eCRFs, Novartis personnel will review the data entered by investigational staff for completeness and accuracy. Electronic data queries stating the nature of the problem and requesting clarification will be created for discrepancies and missing values and sent to the investigational site via the EDC system. Designated investigator site staff is required to respond promptly to queries and to make any necessary changes to the data.

Concomitant treatments and prior medications entered into the database will be coded using the WHO Drug Reference List, which employs the Anatomical Therapeutic Chemical classification system. Medical history/current medical conditions and adverse events will be coded using the Medical dictionary for regulatory activities (MedDRA) terminology.

Samples and/or data will be processed centrally and the results will be sent electronically to Novartis.

Randomization codes and data about all study treatments dispensed to the patient and all IRT assigned dosage changes will be tracked using an Interactive Response Technology. The system will be supplied by a vendor(s), who will also manage the database. The data will be sent electronically to Novartis personnel.

At the conclusion of the study, the occurrence of any emergency code breaks will be determined after return of all code break reports and unused drug supplies to Novartis personnel (or designated CRO). The occurrence of any protocol violations will be determined. After these actions have been completed and the data has been verified to be complete and accurate, the database will be declared locked and the treatment codes will be unblinded and made available for data analysis. Authorization is required prior to making any database changes to locked data, by joint written agreement between the Global Head of Biostatistics and Data Management and the Global Head of Clinical Development.

For EDC studies, after database lock, the investigator will receive a CD-ROM or paper copies of the patient data for archiving at the investigational site.

### **10 Statistical methods and data analysis**

It is planned that the data from all centers participating in the trial will be combined, so that an adequate number of patients are available for analysis. Novartis and/or a designated CRO will perform all analyses. Any data analyses performed independently by any investigator should be submitted to Novartis before publication or presentation.

## **10.1 Analysis sets**

### **10.1.1 Full analysis set**

The full analysis set (FAS) comprises all randomized patients. Following the ITT principle, patients will be analyzed according to the treatment and strata they have been assigned to during the randomization procedure. The FAS will be the primary population for all the efficacy analyses.

### **10.1.2 Safety set**

The Safety Set includes all patients who received at least one dose of study medication defined as tamoxifen/NSAI, goserelin, LEE011 or placebo. Patients will be analyzed according to the study treatment they actually received. Actual treatment refers to the treatment that the patient was randomized to, unless the alternative treatment was received throughout the trial.

### **10.1.3 Per-protocol set**

The per-protocol set (PPS) will include the subset of the patients in the FAS without major protocol deviations. All protocol deviations or conditions leading to exclusion from the PPS will be detailed in the data handling plan and analysis plan. Sensitivity analyses of the primary endpoint of PFS may be performed using data from the PPS if the FAS and PPS differ and if the primary analysis is significant.

### **10.1.5 Crossover analysis set**

The crossover analysis set includes all patients in the placebo arm of the Safety set who elected to crossover to receive LEE011 combination therapy and received at least one dose of LEE011. This population will be used for the analysis of crossover phase data. The crossover phase refers to the time from first dose of LEE011 treatment following crossover until withdrawal from the study or death.

## **10.2 Patient demographics/other baseline characteristics**

Demographic and other baseline data including disease characteristic/prognostic data will be summarized descriptively by treatment group using data from the FAS. Categorical data will be presented as frequencies and percentages. For continuous data, mean, standard deviation, median, 25th and 75th percentiles, minimum, and maximum will be presented.

## **10.3 Treatments (study treatment, concomitant therapies, compliance)**

The safety set will be used for the analyses below.

The actual dose and duration of tamoxifen/NSAI, goserelin, LEE011 and placebo treatment, as well as dose intensity (computed as the ratio of actual dose received to actual duration) and the relative dose intensity (computed as the ratio of the dose intensity to planned dose received/planned duration), will be listed and summarized using descriptive statistics. The total daily doses of tamoxifen/NSAI, goserelin, LEE011 and placebo for each patient will be summarized using descriptive statistics (e.g. mean, median, and mode).

Concomitant medications and significant non-drug therapies will be listed by patient and summarized by ATC (Anatomical therapeutic chemical classification system) term for each treatment group. These summaries will include medications starting on or after the start of study treatment or medications starting prior to the start of study treatment and continuing after the start of study treatment. Any prior concomitant medications or significant non-drug therapies starting and ending prior to the start of study treatment will be listed.

Compliance to the study drug will be assessed by the number of dose reductions and dose interruptions.

The duration of exposure to study treatment and each component of study treatment will also be summarized for the crossover phase in patients who crossed over to LEE011 combination therapy after unblinding (i.e. using the Crossover analysis set).

## **10.4 Primary objective**

The primary objective in the study is to determine whether treatment with tamoxifen or a NSAI + goserelin + LEE011 prolongs PFS compared to treatment with tamoxifen or a NSAI + goserelin + placebo in premenopausal women with HR+, HER2- advanced breast cancer who received no prior hormonal therapy for advanced breast cancer.

### **10.4.1 Variable**

The primary efficacy endpoint of the study is PFS, defined as the time from the date of randomization to the date of the first documented progression or death due to any cause. If a patient has not had an event, PFS will be censored at the date of the last adequate tumor assessment (see RECIST 1.1 in [Appendix 3](#) for further details). Clinical deterioration without objective radiological evidence will not be considered as documented disease progression. PFS will be assessed via a local radiology assessment according to RECIST 1.1. PFS as assessed through blinded independent central review will be used for supportive evidence of the primary efficacy endpoint.

### **10.4.2 Statistical hypothesis, model, and method of analysis**

The primary efficacy analysis will be the comparison of PFS between the two treatment groups using a stratified log-rank test at one-sided 2.5% level of significance.

Assuming proportional hazards model for PFS, the following statistical hypotheses will be tested to address the primary efficacy objective:

$$H_{01}: \theta_1 \geq 0 \text{ vs. } H_{a1}: \theta_1 < 0$$

where  $\theta_1$  is the log-hazard ratio (Tamoxifen or a NSAI+goserelin+LEE011 arm vs. tamoxifen or a NSAI+goserelin + placebo arm) of PFS.

The primary efficacy endpoint PFS will be analyzed based on the FAS according to the treatment group patients were randomized and the strata they were assigned at randomization (strata formed using the randomization factor as obtained via IRT). PFS will be estimated using the Kaplan-Meier method. The median PFS along with 95% confidence intervals will be presented by treatment group. A stratified Cox regression model will be used to estimate the hazard ratio of PFS, along with 95% confidence interval. The primary analysis for PFS will be performed after approximately 329 PFS events have been documented per local assessment.

In addition to the primary analysis in all patients, the treatment effect in terms of PFS for

1. tamoxifen + goserelin + LEE011 vs. tamoxifen + goserelin + placebo, and
2. NSAI + goserelin + LEE011 vs. NSAI + goserelin + placebo

will be estimated using separate Cox regression models. Estimated hazard ratios with corresponding 95% CIs will be presented for each subgroup. PFS will be estimated using Kaplan-Meier methodology within each subgroup.

### 10.4.3 Handling of missing values/censoring/discontinuations

PFS will be censored if no PFS event is observed before the cut-off date. The censoring date will be the date of last adequate tumor assessment before this date. If a PFS event is observed after two or more missing or non-adequate tumor assessments, then PFS will be censored at the last adequate tumor assessment. If a PFS event is observed after a single missing or non-adequate tumor assessment, the actual date of event will be used (see RECIST 1.1 [Appendix 3](#)).

### 10.4.4 Supportive analyses

PFS as assessed by BIRC will be used for supportive evidence of the primary efficacy endpoint. A sample-based BIRC audit approach ([Section 9.3.6](#)) will be used to assess PFS by BIRC. Two methods will be used to summarize the data from the sample-based BIRC assessment of PFS. The NCI (National Cancer Institute) method ([Dodd et al. 2011](#)), uses an auxiliary variable estimator of the log-hazard ratio that combines information from patient-level investigator assessment from all patients and the BIRC assessment of patients randomly selected (see [Section 9.3.6](#)) for central review. This estimate and its one-sided 95% CI will be provided. Details of the sample size calculation for the BIRC assessment are provided in [Section 10.8](#). The NCI method will be used for audit sample size determination and summary of treatment effect (HR, 95% CI) based on the supportive BIRC assessment.

The data from the BIRC assessment generated following the sampling scheme as above will also be summarized using the method proposed by [Amit et al. 2011](#), referred to as the PhRMA (Pharmaceutical Research and Manufacturers of America) method. With this approach, the differential discordance of early discrepancy rate (EDR) and late discrepancy rate (LDR) between the two arms will be estimated as the rate on the tamoxifen or a NSAI+goserelin+LEE011 arm minus the rate on the tamoxifen or a NSAI+goserelin+placebo arm. The EDR and LDR results will also be summarized by treatment arm. Further definitions and details will be provided in the analysis plan.

As a sensitivity analysis, the distribution of PFS will be compared between the treatment groups using an unstratified log-rank test and the hazard ratio along with the associated 95% confidence interval resulting from an unstratified Cox model will be presented.

The primary analysis for PFS may be repeated with data based on the PPS if the primary analysis is statistically significant. A sensitivity analysis will be performed in which PFS is censored at date of the last adequate tumor assessment before any new antineoplastic therapy is started. Other sensitivity analyses may be performed such as (1) including PFS events even if the events are recorded after two or more missed assessments, (2) backdating events occurring after missing tumor assessments.

In addition to the subgroup analyses for patients receiving tamoxifen and those receiving NSAI ([Section 10.4.2](#)), subgroup analyses will be performed on each level of stratification factors if the primary analysis is significant. The analysis will include Kaplan-Meier summaries and estimation of hazard ratios from un-stratified Cox regression models. Additional subgroup analyses to assess the homogeneity of treatment effect based on demographic and baseline disease characteristics may be performed; details about the subgroups to be included will be provided in the study analysis plan.

Patterns of censored data will be examined by the treatment groups using descriptive statistics (the numbers of censored patients and reasons for censoring).

Since the primary endpoint of PFS was met at the time of the primary analysis, no further formal analyses of PFS are planned. If any descriptive analyses of PFS are performed after allowing patients ongoing on study treatment in the placebo arm to crossover to the LEE011 combination arm (permitted after the study had met its primary and key secondary endpoints), appropriate sensitivity analyses will be considered and described in the SAP, for example censoring PFS at the last adequate tumor assessment prior to crossover for patients in the crossover analysis set.

## 10.5 Secondary objectives

The secondary objectives in this study are to compare the two treatment groups with respect to OS, and evaluate ORR, CBR, time to response, duration of response, time to definitive deterioration in the quality of life and ECOG PS, and safety. OS is identified as the key secondary endpoint. A hierarchical testing strategy will be taken to control overall type-I error rate; therefore OS will be statistically evaluated and interpreted only if the primary efficacy endpoint PFS is significantly different between the 2 treatment groups.

### 10.5.1 Key secondary objective(s)

The key secondary objective of the study is to determine whether treatment with tamoxifen or a NSAI + goserelin + LEE011 prolongs OS compared to treatment with tamoxifen or a NSAI + goserelin + placebo.

OS is defined as the time from date of randomization to date of death due to any cause. If a patient is not known to have died, then OS will be censored at the date of last known date patient alive.

Assuming proportional hazards model for OS, the following statistical hypothesis for OS will be tested using a stratified log-rank test (stratified according to randomization stratification factors) at the one-sided 2.5% level of significance:

$$H_{02}: \theta_2 \geq 0 \text{ vs. } H_{a2}: \theta_2 < 0$$

where  $\theta_2$  is the log-hazard ratio (tamoxifen or a NSAI+goserelin+LEE011 arm vs. tamoxifen or a NSAI+goserelin+placebo arm) of OS.

The analyses for OS will be based on the FAS. The distribution of OS will be compared between the two treatment groups using a stratified log-rank test at one-sided 2.5% level of significance.

The final OS analysis will not be performed at the time point of the primary PFS analysis, but after additional follow-up. Therefore, a three-look design is considered for OS.

OS will be hierarchically tested in the following way:

1. The first potential time point for OS analysis will be at the time of the primary PFS analysis, when 123 deaths are expected. If PFS is statistically significant at this stage, OS will also be tested.
2. If OS is not statistically significant at this stage, the 2nd OS analysis will be planned after approximately 189 deaths.

3. If OS is not statistically significant at this stage, a final analysis is planned after approximately 252 deaths have been recorded.
4. If PFS is not statistically significant at the primary analysis, then OS will not be tested.

The type I error probability for OS tests will be controlled by using a Lan-DeMets (O'Brien-Fleming) alpha spending function at the one-sided type I error of  $\alpha=0.025$ . This guarantees the protection of the overall level  $\alpha = 2.5\%$  across the two hypotheses and the repeated testing of the OS hypotheses in the interim and the final analyses (Glimm 2010).

The distribution function of OS will be estimated using the Kaplan-Meier method. The median OS along with 95% confidence intervals will be presented by treatment group. The stratified Cox regression will be used to estimate the hazard ratio (HR) of OS, along with 95% confidence interval.

Since the key secondary endpoint of OS was met at the second interim analysis, no further formal analyses of OS are planned. If any descriptive analyses of OS are performed after allowing patients ongoing on study treatment in the placebo arm to crossover to the LEE011 combination arm (permitted after the study met its primary and key secondary endpoints), appropriate sensitivity analyses will be considered and described in the SAP, for example censoring OS at the date of first LEE011 treatment for patients in the crossover analysis set.

## **10.5.2 Other secondary efficacy objectives**

### **10.5.2.1 Overall response rate**

Overall response rate is defined as the proportion of patients with best overall response (BOR) of complete response (CR) or partial response (PR) according to RECIST 1.1.

ORR will be calculated based on the FAS according to the ITT principle; however patients with only non-measurable disease at baseline will be included in the numerator if they achieve a complete response. ORR will be presented by treatment group along with approximate 95% confidence intervals. The Cochran-Mantel Haenszel chi-square test (stratified by baseline stratification factors) will be used to compare the two treatment groups with respect to the ORR at one-sided 2.5% level of significance. As a supportive analysis, ORR as assessed by the blinded independent central review will be calculated by treatment group and presented along with the approximate 95% confidence intervals. As a sensitivity analysis, ORR for patients with measurable disease at baseline will be calculated and presented by treatment group together with approximate 95% confidence intervals.

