### **10.5.2.2 Clinical benefit rate**

Clinical Benefit is defined as CR or PR, or SD for 24 weeks or longer. CR, PR and SD are defined according to RECIST 1.1. CBR will be calculated based on the FAS; however patients with only non-measurable disease at baseline will be included in the numerator if they achieve a complete response. CBR will be summarized for the two treatment groups using descriptive statistics. The Cochran-Mantel Haenszel chi-square test (stratified by baseline stratification factor) at 2.5% one-sided level of significance, will be used to compare the two treatment groups with respect to the CBR. As a supportive analysis, CBR as assessed by the blinded independent central review will be summarized for the two treatment groups using descriptive statistics.

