### **10.5.2.5 ECOG performance status**

ECOG PS scale as described in [Table 7-3](#) will be used to assess physical health of patients. An analysis of time to definitive deterioration of the ECOG PS by one category of the score from baseline will be performed using the FAS. Deterioration is considered definitive if no improvement in ECOG PS is observed at a subsequent time of measurement during the treatment period following the time point where the deterioration is observed.

Patients that have not worsened at the data cut-off point will be censored at the date of last assessment prior to data cut-off. Kaplan-Meier method will be used to estimate the distribution of time to definitive worsening and median time to definitive worsening will be presented along with a 95% confidence interval. A stratified log-rank test at one-sided 2.5% level of significance will be used to compare the distribution of time to definitive worsening between the 2 treatment arms.

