3.8.2 Secondary efficacy analyses

The secondary efficacy objectives in this study are to

- compare the two treatment arms with respect to overall survival
- evaluate the two treatment arms with respect to overall response rate and clinical benefit rate;
- describe time to response and duration of response in each treatment arm;
- evaluate the two treatment arms with respect to time to deterioration of ECOG Performance Status;
- evaluate patient reported outcomes for health-related quality of life in the two treatment arms.

OS is the key secondary endpoint. A hierarchical testing strategy, where OS is to be statistically evaluated and interpreted only if the primary efficacy endpoint PFS is statistically significant favoring the treatment arm, will be used to control the overall type-I error rate.

The analysis of all secondary efficacy endpoints will be performed based on the FAS.

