3.8.2.2 Overall response rate

ORR is defined as the proportion of patients with best overall response of confirmed complete response (CR) or confirmed partial response (PR) according to RECIST 1.1 (see Appendix 3 of the study protocol). ORR will be calculated based on the FAS using investigators' review of tumor assessment data. Patients with only non-measurable disease at baseline will be part of the analysis and will be included in the numerator only if a complete response was observed. ORR will be presented by treatment arm along with standard Wald asymptotic (i.e. normal approximation) 95% confidence intervals. The Cochran-Mantel Haenszel chi-square test (strata based on IRT data) will be used to compare the two treatment arms with respect to the ORR at a one-sided 2.5% level of significance.

As sensitivity analysis, ORR will be calculated and summarized including only patients with measurable disease at baseline.

As a supportive analysis, ORR will also be summarized based on the BIRC review of tumor data. However, no p-value will be presented.

Clinical benefit rate

CBR is defined as the proportion of patients with a best overall response of confirmed CR or PR, or SD lasting 24 weeks or longer, according to RECIST 1.1 criteria. A patient will be considered to have SD for 24 weeks or longer if a SD response is recorded at 24-1=23 weeks or later from randomization, allowing for the ± 1 week visit window for tumor assessments. Patients with only non-measurable disease at baseline will be part of the analysis and will be

included in the numerator only if they achieve a complete response or have a ‘Non-CR/Non-PD’ response 23 weeks or more after randomization. CBR will be calculated using the FAS based on the investigators’ tumor assessments. CBR will be summarized for the two treatment arms using descriptive statistics. The Cochran-Mantel-Haenszel test (strata based on IRT data) at one sided 2.5% level of significance will be used to compare the two treatment arms with respect to CBR.

As a sensitivity analysis, the above analyses will be repeated including only patients with measurable disease at baseline.

As a supportive analysis, CBR based on BIRC data will be summarized for the two treatment arms using descriptive statistics but no p-value.

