If a definitive deterioration is observed after two or more missing assessments (using an analogous rule to that defined for PFS in [Section 2.5.5](#), based on the windows specified above),

time to deterioration will be censored at the date of the last ECOG PS assessment prior to the deterioration.

Patients receiving any further anti-neoplastic therapy before definitive deterioration will be censored at the date of their last assessment before the start date of the therapy. Patients that have not deteriorated as of the cutoff date will be censored at the date of their last assessment before the cutoff.

Kaplan-Meier estimates will be constructed for each treatment arm. The median, 25th and 75th percentiles for time to definitive deterioration for each treatment group will be obtained along with 95% confidence intervals.

A stratified log-rank test at one-sided 2.5% level of significance will be used to test the difference in time to definitive deterioration of performance status between treatment arms. A (stratified) Cox proportional hazards model will be used to estimate the hazard ratio (with 95% confidence interval).

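### ORR, CBR and time to ECOG deterioration are each tested at the full one-sided 2.5% outside the PFS-then-OS hierarchy, with no gate, order, alpha split or nominal label

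*Protocol*

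**What the plan says.** Protocol 10.5 lists OS, ORR, CBR, response times, quality of life, ECOG performance status and safety together as secondary objectives, and then says: "A hierarchical testing strategy will be taken to control overall type-I error rate". SAP 3.8.2 (the primary-analysis SAP, based on protocol amendment 4) gives a similar list of secondary efficacy objectives and says that the hierarchy "will be used to control the overall type-I error rate".

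The hierarchy has two members. Protocol 10.5.1 and 10.7.2 and SAP 3.14.2 test OS only if PFS is significant, and limit the 2.5% guarantee to those two hypotheses and the repeated OS looks.

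Three more endpoints are then given a test and a level:

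- ORR: a stratified Cochran-Mantel-Haenszel test "will be used to compare the two treatment groups with respect to the ORR at one-sided 2.5% level of significance" (Protocol 10.5.2.1). SAP 3.8.2.2 agrees: "will be used to compare the two treatment arms with respect to the ORR at a one-sided 2.5% level of significance".
- CBR: the same test, "at 2.5% one-sided level of significance, will be used to compare the two treatment groups with respect to the CBR" (Protocol 10.5.2.2). The CBR part of the SAP agrees and repeats the analysis in patients with measurable disease.
- ECOG: "A stratified log-rank test at one-sided 2.5% level of significance will be used to compare the distribution of time to definitive worsening" (Protocol 10.5.2.5). SAP 3.8.2.5 has: "A stratified log-rank test at one-sided 2.5% level of significance will be used to test the difference in time to definitive deterioration".

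For patient-reported outcomes, Protocol 10.5.4 says that there will be no formal tests and, for that reason, no multiplicity adjustment. SAP 3.8.2.6 instead compares time to 10% deterioration by stratified log-rank test at one-sided 2.5%, for global health status and for the secondary scales of interest.

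**The concern.** The primary PFS comparison is specified as "using a stratified log-rank test at one-sided 2.5% level of significance" (Protocol 10.4.2), and OS is specified in nearly the same terms. ORR, CBR and ECOG carry the same level in the same form of words, so the wording does not show which tests are confirmatory.

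Elsewhere the plan does mark the difference. The SAP makes no inferential comparison for time to response or duration of response, and gives no p-value for the BIRC response summaries or the by-stratum PFS results. Protocol 10.5.4 ties the absence of multiplicity adjustment to the absence of formal testing. By that logic three formal tests call for some handling, and none is given.

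At stake is how results are labelled. A one-sided p-value of 0.02 on CBR or ECOG deterioration meets the level that the plan sets and could be reported as significant, under a section that opens with control of the overall error rate but does not extend it to that test.

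**Working it through.** **1. The plan's own figure.** The 2.5% for PFS and OS reproduces.

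- PFS, 329 events, HR 0.67, one-sided 0.025 (Protocol 10.8): power = Φ(|ln 0.67| × √329 / 2 − 1.96) = 95.3%, against 95% stated.
- OS, 123, 189 and 252 deaths (Protocol 10.7.2), with the SAP 4.3.1 spending function 2 − 2Φ(z/√t), z the upper 1.25% normal point and t = 123/252, 189/252 and 1: cumulative alpha 0.00134, 0.00965 and 0.02500; boundaries 3.00, 2.36 and 2.01. Cumulative power at HR 0.7 is 15.3%, 54.1% and 80.1%, against 15, 54 and 80 in Protocol Table 10-1.
- Hierarchy: if PFS is null, an error requires a false PFS rejection (2.5%). If PFS is real and OS null, the OS design spends 2.5%. The guarantee holds for both hypotheses.

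**2. The three ungated tests.** Suppose the PFS and OS effects are real and ORR, CBR and ECOG are null. With k independent tests at 0.025, P(at least one false rejection) = 1 − 0.975^k. For k = 3 this is 1 − 0.9269 = 7.3%; the Bonferroni bound is 3 × 2.5% = 7.5%.

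**3. Full null.** OS can be rejected only after PFS, so the hierarchy counts as one further test at 2.5%. For k = 4, 1 − 0.9037 = 9.6%.

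**4. Correlation.** The documents give none, so it is an assumption. With an equal correlation ρ between all test statistics, the rate is one minus the multivariate normal probability that every Z is at most 1.96:

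| ρ | three tests | PFS gate plus three |
|---|---|---|
| 0 | 7.3% | 9.6% |
| 0.3 | 6.8% | 8.7% |
| 0.5 | 6.3% | 7.8% |
| 0.7 | 5.5% | 6.5% |
| 0.9 | 4.2% | 4.7% |

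Only the ORR–CBR pair can be informed from the documents, because response is nested in clinical benefit: correlation = √[p(1 − q) / ((1 − p)q)], with p the response rate and q the benefit rate. The first-line anastrozole row of Protocol Table 1-1 with p = 0.36 and q = 0.67 gives √(0.1188 / 0.4288) = 0.53. The anastrozole and letrozole rows together span about 0.15 to 0.83. With ORR–CBR correlation 0.3 to 0.8 and ECOG correlation 0 to 0.6, the three-test figure is 5.5% to 7.1%.

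**5. Patient-reported outcomes.** SAP 3.8.2.6 names one primary scale (global health status) and five secondary ones (physical, emotional and social functioning, breast cancer symptoms, EQ-5D-5L visual analog scale). That makes 3 + 6 = 9 ungated tests. If all nine were null and independent, 1 − 0.975^9 = 20.4%. This is an upper-end value, because scales from the same questionnaires are positively correlated.

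**The case against.** The strongest reply is that the control statement already has a stated scope. Protocol 10.5.1 and 10.7.2 confine the guarantee to PFS and OS. Null and alternative hypotheses are written only for those two. Protocol Table 3-1 separates the key secondary objective from the others, which are to be evaluated or described. Nothing expressly permits a claim on ORR, CBR or ECOG. All of this stands. A reader might infer that the 2.5% guarantee is false; the documents do not support that, since it is limited to two hypotheses and is exact for them.

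A reader might also infer that p = 0.02 on one of these endpoints could support no claim under any familywise control at 2.5%. That is wrong too. In a pre-specified fixed sequence after OS, each endpoint would be tested at the full 2.5% once all earlier hypotheses were rejected. The difficulty is that the plan sets no such sequence.

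Finally, timing. Amendment 7 records that PFS and OS were both met and makes later analyses descriptive (Protocol 10.7.2). The final-report SAP contains no efficacy tests. So the full-null figures no longer describe a live case, and the practical reach is the labelling of results from the primary-analysis SAP and of any later efficacy update. This limits the consequence but does not supply the missing label.

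**Conclusion.** The point holds as a gap in labelling and scope. Three other secondary endpoints have formal tests at the full one-sided 2.5%, outside the only multiplicity control in the plan, and the opening statements of Protocol 10.5 and SAP 3.8.2 read wider than the guarantee that follows. PFS and OS inference, boundaries and power are untouched.

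With PFS and OS effects real and the three endpoints null, the chance of at least one false significant result is 7.3% under independence and 4.2% to 7.3% for equal correlations of 0.9 to 0. Under the full null it is 4.7% to 9.6%. A single narrower figure would need a correlation near 0.5 for every pair, and the documents support no such value for ECOG or PFS.

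Separately, SAP 3.8.2.6 and Protocol 10.5.4 contradict each other on whether patient-reported outcomes are formally tested.

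**What to change.** In Protocol 10.5.2.1, 10.5.2.2 and 10.5.2.5, and in the matching ORR, CBR and ECOG parts of the primary-analysis SAP, remove the significance level. Say instead that a nominal one-sided p-value is reported with the estimate and 95% confidence interval, that it lies outside the type I error control, and that no claim of statistical significance rests on it. State in Protocol 10.5 and SAP 3.8.2 that control covers PFS and OS only. Reconcile SAP 3.8.2.6 with Protocol 10.5.4, giving any patient-reported p-values the same nominal status.

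Placing the three endpoints in a fixed order after OS would also have held the rate at 2.5%, but only if set before unblinding. Since PFS and OS have been reported, the nominal label is the change that still applies.

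The cost is wording and table footnotes, with no new data or analyses and no loss of power for PFS or OS. The downside is that these endpoints can no longer be described as statistically significant.
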